1. BACKGROUND INFORMATIONS AND RATIONALE

1.1. CUTANEOUS SQUAMOUS CELL CARCINOMA

Cutaneous squamous cell carcinoma (cSCC) is the second most common form of skin cancer and derives from keratinocytes. It accounts for 20% of skin cancers but recently studies show a rising of incidence, therefore reducing the difference with basal cell carcinoma (BCC). cSCC is more frequent in Caucasian population and the most frequent site is head and neck. The most significant risk factors are age (it is more common from 60 years), fair skin, hair and eyes, sun exposure or indoor tanning. A very important risk factor is immunosuppression, particularly in patients who received a solid organ transplant, with a history of hematological malignancies or in patients with chronic immunosuppressive therapy because of autoimmune diseases. In these cases, the risk is from 5 to 100-fold higher. Usually, cSCC is diagnosed at an early stage as localized disease, more rarely it is diagnosed as locally advanced or metastatic at diagnosis. For local cSCC the goal is a radical surgery that could be a classical surgical excision or a Mohs Micrographic Surgery. In any case, for radical intent, margins must be negative. In particular, margins should be from 4 mm wide to 10 mm according to the risk of primary lesion. So far, there is no consensus about sentinel lymphnode role, due to the small number of patients enrolled in clinical studies aimed at evaluating this therapeutic strategy. After histopathological confirmation of cSCC, an important step is to establish the risk of recurrence. cSCC patients need to be distinguished as having low or high risk of recurrence on the basis of several clinical and histopathological risk factors. In fact, in case of high risk cSCC further adjuvant treatment should be evaluated in multidisciplinary discussion.

The following factors should lead to consider the employment of adjuvant radiotherapy in the setting of operated cSCC:

- close or positive margins that cannot be corrected with further surgery (secondary to morbidity or adverse cosmetic outcome)
- gross perineural spread
- setting of recurrence after a prior margin-negative resection
- stage T3 and T4
- desmoplastic or infiltrative tumors in the setting of chronic immunosuppression
- at pathological exam, cSCC involving regional lymphnodes, with the exception of a single, small (<3 cm) cervical lymph node harboring carcinoma, without extracapsular extension.

In terms of cSCC staging there are two major classification systems: the AJCC (American Joint Committee on Cancer) 8th edition that considered T stage and N stage and the BWH (Brigham and Women's Hospital) that considers only T stage.

An alternative to surgery for inoperable or difficult to operate cSCC is primary radiotherapy (RT). Another application of RT is the adjuvant setting. It is used as clinical practice for operated cSCC with positive margins where there is not space for re-surgery or in case of high risk cSCC, in particular showing extensive perineural or large nerve involvement, or in patients with positive nodes (particularly with extracapsular extension). Unfortunately, the value of adjuvant RT is still debated due to the lack of randomized prospective trials. The application of immunotherapy with anti-PD1 agents in adjuvant setting is a new investigation field. Trials are ongoing to evaluate the efficacy of immune-agents in high risk cSCC after RT.

For locally advanced, recurrent and metastatic cSCC, systemic treatments could be used. An important study field is the application of immunotherapy in this kind of patients. The rationale behind treating cSCC with anti-PD1 agents is based on different reasons. Primarily, cSCC are radiation induced tumors so they exhibit a high tumor mutational burden (TMB) that may act as neo-antigen in stimulating cytotoxic T cells. Secondly, the disease is strongly associated with immunosuppression. Several studies with anti-PD1 were conducted till cemiplimab was approved in first line setting for locally advanced and metastatic cSCC showing a huge, rapid and durable response (ORR about 50%) with an acceptable rate of adverse events. Pembrolizumab is another immune checkpoint inhibitor employed in cSCC.

Considering other systemic treatments, epidermal growth factor receptor inhibitors were tested. Cetuximab is an intravenous EGFRi showing responses in locally advanced or recurrent/metastatic head and neck cancers in combination with RT or chemotherapy, respectively. Also, classic chemotherapy regimen based on cisplatin, carboplatin, 5-FU and taxanes in monotherapy or in combination therapy were administered in advanced setting. Efficacy data were derived from small case series and a limited number of randomized trials. With these systemic agents, duration of response is limited and toxicity is often an issue when treating elderly patients with multiple comorbidities (1-2-3-4-5).

1.2. CLINICAL APPLICATION OF ADJUVANT RADIOTHERAPY IN cSCC

The value of adjuvant RT is still debated due to the lack of randomized prospective trials, however, there is general consensus on its added value after surgery for high-risk cSCC. As demonstrated in the phase 3 randomized TROG 05.01 trial, the combination of surgery and adjuvant RT results in a sustained rate of loco-regional control (88% and 82% in the control arm of the study at 2 and 5 years, respectively) (6). Large retrospective data from tertiary centers also point towards a survival benefit associated with RT receipt, particularly for those patients with perineural invasion and regional disease (7). Overall, there are some condition defined at high risk in which radiotherapy is performed as post-operative treatment. The principal risk factors that should be considered for post-operative

radiation treatment are the presence of positive margin after surgery, nodal involvement, perineural invasion and lympho-vascular invasion. Other prognostic factors are site of disease, poorly differentiation, type of histology and recurrence.

Usually, post-operative radiation therapy consists of a minimum biologically Equivalent Dose of 2 Gy per fraction to the site of primary disease for a total dose of 50-54 or 60-66 Gy depending on the margin status.

The Head and Neck Cancer International Group (HNCIG) Consensus Guidelines (8) should be regarded as the reference paper for the delivery of postoperative RT in high-risk cutaneous squamous cell carcinoma of the head and neck. Briefly, a high-risk tumor volume for the primary tumor (CTVp_HR) and nodal disease (CTVn_HR) should be recognized in the delineation phase based on all clinical, radiological and pathological findings, enlarged of a 5-mm margin (edited for anatomical barriers) and be targeted to a total dose of 60 Gy at conventional fractionation, whereas those areas deemed at substantial risk of microscopic disease such as positive surgical margin or pathologic lymphnodes with extranodal extension may warrant a boost dose up to 66 Gy (CTVp_HR_Boost or CTVn_HR_Boost). All those areas deemed at low risk of harboring microscopic disease should be encompassed within the low-risk tumor volume, both for the primary and nodal disease (CTVp_LR and CTn_LR, respectively). Simulation, treatment planning, treatment delivery and verification should be performed according to standard practice. Intensity-modulated radiation therapy (IMRT) should be regarded as the minimum technical requirement. As suggested by the HNCIG consensus guidelines, when IMRT is used, a common treatment schedule employing a simultaneous-integrated boost (SIB) technique may consist of a 30-fraction course whereby 63 Gy, 60 Gy and 56 Gy are delivered to the PTV_boost, PTV_HR and PTV_LR, respectively.

Radiation therapy can cause several side effects such as rashes, dry, itchy and frail skin, photosensitivity, oedema, fatigue. For head and neck treatment frequent adverse events are also sore throat, dry mouth, cough and difficult swallowing (9).

1.3. IMMUNE SYSTEM IN cSCC AND IMMUNO-MODULATING EFFECTS OF RADIOTHERAPY

[figure not shown]
cSCC is a neoplasm strictly related to immunosuppression: in this context, cSCC could be multiple, recurrent and more aggressive. This statement highlights the importance to study the relationship between this tumor and circulating immune-cell and tumor microenvironment (TME). The immune mechanisms involved in tumors development are complex and related to the interplay of immunosurveillance/immunoediting and the TME that is characterized by dynamic intercellular communications via networks of chemokines, cytokines, growth factors and inflammatory remodeling enzymes. A lot of immune-circulating cells are involved in tumor growth control and in cSCC development, as neutrophil, T lymphocytes (CD8 and CD4, natural killer cells), B lymphocytes, dendritic cells, myeloid-derived suppressor cells, chemokines and cytokines (IL-6, IL-10, IL-2, IFN- γ , TGF- β) (10). This equilibrium between TME and circulating immune cells plays an important role

in patient's outcome. Moreover, oncologic treatments as chemotherapy and radiotherapy modifies and influences patient's immune system. In particular, several retrospective studies demonstrated the alterations induced by radiotherapy in different cancer subtypes and their effects on outcome. In patients affected from pancreatic, head and neck, non-small cell lung cancer and cervical cancer, radiation or chemoradiation treatments induced lymphopenia (defined as lymphocytes < 500) and the occurrence of elevated neutrophil- to- lymphocytes ratio in many patients who were characterized from worse prognosis in terms of reduced progression or disease-free survival and overall survival. Furthermore, worse outcomes were related to dose, volume and site of irradiation. For non-small cell lung cancer a connection between radiation-induced lymphopenia and Gal-1 secretion was found. Even if there are not in literature studies evaluating the relation between lymphopenia and cSCC, we can hypothesises that the same scenario could interest patients affected from neoplasm as cSCC that is also particularly dependent from patient's immune system. (11-12).

The relation between immune system and neoplasm has become an important field of research with immunotherapy development in these last few years. Radiotherapy causes modifications on circulating immune cells and TME. In fact, irradiation provokes endothelial cells damages and inflammation causing inhibition of CD8+ T lymphocytes infiltration into tumors and immunosuppressive pathways activation. This immunosuppressive effect is represented by accumulation of radioresistant suppressor cells as macrophages, myeloid-derived suppressors cells, and regulatory T cells. But, on the other hand, irradiation can also activate the immune response through release and presentation of antigens, priming and activation of T lymphocytes, recruitment and accumulation of T cells in the tumor, enhancing inflammation and increasing IFN- γ expression (13-14). So, radiotherapy effect on immune system and TME is very complex and two-fold.

We lack studies evaluating the interplay between immune system and cSCC before and after radiation treatment, investigating the effect on TME. The aim of this study is to evaluate the effect of radiotherapy-induced lymphopenia in cSCC on outcomes and radiotherapy modifications in terms of changes in the profile of circulating immune cells.

Fig. 1 The two-fold effect of radiotherapy on cancer cells and TME

1.4 MOLECULAR ASPECTS OF cSCC

The most significant risk factors involved in cSCC pathogenesis are sun exposure, UV rays and indoor tanning. These elements are associated with elevated tumor mutational burden (TMB). It is well known that cSCC carries more mutation than other common cancer (5 times the mutation rates in lung cancer and 4 times in melanoma) but, nowadays, there are not validated evaluations and classifications that takes into account a molecular profile of cSCC. Targeting TMB in cSCC could be an instrument to classify these tumors in different levels of risk of recurrence and/or metastatic spread. The cSCC risk profile is only based on clinic-pathological risk factors listed in NCCN Guidelines. The integration between clinical-pathological risk factors and molecular or immunological tumor profiles may improve the prognostic ability and consequently may refine management of localized lesions. This could prompt to tailor adjuvant treatments and define personalized follow up programs.

A 40-gene expression signature test has been recently developed and validated. It classifies patients with cSCC into three groups: low risk of recurrence, high risk and highest risk, for this latter category the positive predictive value is 60%. Many of the discriminant genes comprises in the test have been previously reported in cSCC and/or have known function in cancer pathways.

The application of this test could be another step to better classify cSCC and to choose a more adequate post-operative treatment based on molecular risk of recurrence. (15-16-17)

Fig. 2 Some of discriminant genes included in the 40 gene expression panel.

GENE ID	GENE NAME	SOURCE
ACSBG1	Long-chain-fatty-acid--CoA ligase ACSBG1	1
ALOX12	Arachidonate 12-Lipoxygenase, 12S Type	1
APOBEC3G	Apolipoprotein B mRNA Editing Enzyme Catalytic Subunit 3G	1
ATP6V0E2	ATPase H+ Transporting V0 Subunit E2	1
BBC3	Bcl-2-binding component 3	2
BHLHB9	Basic Helix-Loop-Helix Family Member B9	8
CEP76	Centrosomal protein of 76 kDa	1
DUXAP9	Double Homeobox A Pseudogene 9	8
GTPBP2	GTP Binding Protein 2	8
HDDC3	Guanosine-3',5'-bis(diphosphate) 3'-pyrophosphohydrolase MESH1	8
ID2	Inhibitor Of DNA Binding 2	3
LCE2B	Late Cornified Envelope 2B	1
LIME1	Lck Interacting Transmembrane Adaptor 1	8
LOC100287896	Uncharacterized LOC100287896	8
LOC101927502	Uncharacterized LOC101927502	8
MMP10	Matrix Metalloproteinase 10 (Stromelysin 2)	1, 4, 5
MRC1	Mannose Receptor C-Type 1	6, 7
MSANTD4	Myb/SANT DNA Binding Domain Containing 4 With Coiled-Coils	8
NFASC	Neurofascin	1
NFIC	Nuclear Factor I C	8
PDPN	Podoplanin	1
PI3	Peptidase Inhibitor 3	1, 4
PLS3	Plastin 3	8
RCHY1	Ring Finger And CHY Zinc Finger Domain Containing 1	2
RNF135	Ring Finger Protein 135	8
RPP38	Ribonuclease P/MRP Subunit P38	8
RUNX3	Runt-Related Transcription Factor 3	8
SLC1A3	Solute Carrier Family 1 Member 3	8
SPP1	Osteopontin	1
TAF6L	TATA-Box Binding Protein Associated Factor 6 Like	8
TFAP2B	Transcription Factor AP-2 Beta	1
ZNF48	Zinc Finger Protein 48	8
ZNF496	Zinc Finger Protein 496	8
ZNF839	Zinc Finger Protein 839	8

1.5. RATIONALE FOR STUDY DESIGN

Treatment with adjuvant radiotherapy modulates immune system in many diseases as witnessed by dynamic changes of humoral and cellular immunity. Moreover, the persistent lymphopenia after radiation therapy is a negative prognostic factor. This study is aimed to explore the changes in immune-cell populations during radiotherapy given as adjuvant treatment for high-risk cutaneous squamous cell carcinomas and to correlate them with patient's outcome.

2. STUDY OBJECTIVES AND OUTCOMES

2.1.1. Primary objective

The primary endpoint is to evaluate the impact of diminished ALC (Absolute Lymphocyte Counts) after RT on patient's outcome.

2.1.2. Primary outcome

Primary outcome consists of disease-free survival (DFS) of patients with ALC < 500 cells/mL after radiotherapy treatment.

2.2.1. Secondary objectives

Secondary objectives include:

- Evaluation of changes (Δ) in the circulating immune-cells population at two time points (before and after RT);
- Correlation between DFS and circulating immune cell population before and after RT;
- Evaluation of changes in immune cell population according to the primary site (h&n vs non-h&n), volume (cc) and administered dose (50 Gy; 50-60 Gy; >60 Gy depending on margins involvement) of irradiation. The same parameters will be evaluated according to the nodal basin irradiation in terms of levels included in CTV-HR vs CTV-LR (levels, volume and dose).
- Evaluation of changes (Δ) in the circulating immune-cells population in the subgroup of patients defined as "immunosuppressed" (i.e. patients with chronic hematologic malignant neoplasm, or HIV, or AIDS, or who were treated with immunosuppressive therapies for organ transplantation 6 months or more prior to diagnosis) in respect of non-immunosuppressed patients;
- Evaluation of changes (Δ) in the circulating immune-cells population according to RT induced toxicities;
- 2-year Overall Survival (OS)

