2.2.2. Secondary outcome

Secondary outcomes include:

- Changes in white cells blood sub-population defined by the difference between two time points: the day before adjuvant RT (day -1) to day 28 (+/- 3 days) after RT.

In particular, we will evaluate changes of:

- circulating T cells CD3+CD8+ and CD3+CD4+

- absolute lymphocyte count (ALC) and neutrophil counts (ANC) and neutrophil/lymphocyte ratio (NLR)
- Treg lymphocytes, defined as CD4+CD25+FOXP3+ or CD4+CD25hi+CD39+ cells.
- Naïve/Memory T lymphocytes CD4+ and CD8+ (defined as CD45RA/CD45RO)
- myeloid-derived suppressor cells, defined as cells expressing Lin-neg (CD3, CD14, CD15, CD19, CD56) /HLA-DR-/CD33+/CD11b+ in either a “lymphocyte” (small FSCxSSC) gate, or in a “monocyte” (larger FSCxSSC) gate, and as HLA-DR+/lo CD14+ cells in a large gate.
- Plasmacytoid Dendritic Cells (CD303+CD123+)
- NK cells dim (CD3-CD16+CD56+) and bright (CD3-CD16-CD56++);
- NKT cells (CD3+CD56+);
- Myeloid Dendritic cells (CD1c+ and CD141+);
- Monocytes subsets (classical CD14+CD16-, intermediate CD14+CD16+, non classical CD14+/-CD16+);
- B lymphocytes (CD19)
- Analysis of plasma cytokines (TNFalpha, TGFbeta, IL-6, IL-10) by ELISA;
- IFN signature: real-time PCR on mRNA from peripheral blood mononuclear cells (PBMCs)

- DFS of patients according to the values of the above reported immune population at baseline, after RT and according to the changes before/after RT

- Changes in immune population cell at the two time points according to the following variables:

- Site of irradiation (involving or not nodal basins, head and neck vs non-head and neck area and lymphnodes levels involved in CTV-HR vs CTV-LR)
- Volume of irradiation (expressed as cc) for primary site and nodal basin (volume received by lymphnodes classified as CTV-HR vs CTV-LR)
- Dose of irradiation (total dose received in Gy) for primary site (depending on the margin status) and nodal basin (dose received by lymphnodes classified as CTV-HR vs CTV-LR)

- Changes in immune population cells in the immunosuppressed patient subgroup in comparison with non-immunosuppressed patients

- Changes in immune population cells according to RT related toxicities as mucositis and radiodermatitis

- 2-year OS

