3.2. Exclusion criteria

1. cSCC not eligible for surgery
2. cSCC not eligible for adjuvant radiotherapy for any condition depending on disease characteristics or patient characteristics, co-morbidities or refusal
3. Any concurrent investigational product, biologic, or hormonal therapy for cancer treatment
4. Concurrent treatment with chemotherapy for the purpose of cSCC cure
5. History or current evidence of any condition that, in the opinion of the treating investigator, might interfere with the subject's participation for the full duration of the trial.
6. Any major surgery, different from that planned for the protocol, in the 15 days before the protocol starting
7. Any radiotherapy treatment in the 28 days before the protocol starting
8. Pregnant or breastfeeding.

NB: patients with chronic hematological malignancies with or without ongoing treatment or patients with autoimmune diseases will be eligible for the study. They will be analyzed both in the whole series of patients and as a separate subgroup.

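### The immunosuppressed subgroup in section 2.2.1 omits immunosuppressive therapy for autoimmune disease, so by its two-way split such patients fall into the non-immunosuppressed comparator

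*Combined protocol and SAP*

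**What the plan says.** Section 2.2.1 sets out a comparison of immune-cell change between immunosuppressed patients and the rest. It introduces the definition with i.e., so the list reads as complete: "patients with chronic hematologic malignant neoplasm, or HIV, or AIDS, or who were treated with immunosuppressive therapies for organ transplantation 6 months or more" before diagnosis. The comparison is made "in respect of non-immunosuppressed patients". Section 2.2.2 repeats it as an outcome: "Changes in immune population cells in the immunosuppressed patient subgroup in comparison with non-immunosuppressed patients". Neither section has a third category.

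Three other places bear on who counts as immunosuppressed:

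- **Section 1.1** presents immunosuppression as a risk factor and names solid organ transplant recipients, then patients "with a history of hematological malignancies or in patients with chronic immunosuppressive therapy because of autoimmune diseases".
- **Section 3.1, criterion 4**, includes chronic immunosuppression, with no limit on its cause, as the setting in which desmoplastic or infiltrative tumours qualify as high risk.
- **The note closing section 3.2** says that "patients with chronic hematological malignancies with or without ongoing treatment or patients with autoimmune diseases will be eligible for the study" and adds: "They will be analyzed both in the whole series of patients and as a separate subgroup".

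Sections 5.2 and 5.3 do not prohibit immunosuppressive drugs. Section 10 does not mention the immunosuppressed subgroup.

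**The concern.** The background names three kinds of immunosuppressed patient, and the analysis definition keeps two of them and drops the third without giving a reason. A patient could enter the study because the tumour arose under chronic immunosuppression for an autoimmune disease, and then be analysed as non-immunosuppressed.

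The comparison asks whether immune cells respond differently to radiotherapy when the immune system is already suppressed. Pharmacologically suppressed patients in the reference group blur the contrast under study. The 3.2 note also describes a subgroup that shares only haematological malignancy with the 2.2.1 list. With two memberships in the plan and no statement of how they relate, the choice between them could be made after the data are seen.

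**Working it through.** **Side by side**

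| Condition | 1.1 background | 2.2.1 subgroup | 3.2 note |
|---|---|---|---|
| Haematological malignancy | yes | yes (chronic) | yes (chronic) |
| Organ transplant | yes | yes (on immunosuppression) | no |
| HIV or AIDS | not named | yes | no |
| Immunosuppressive therapy for autoimmune disease | yes | no | only as part of autoimmune disease in general |
| Autoimmune disease without such therapy | no | no | yes |

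Take a patient on systemic immunosuppressants for autoimmune disease with no other listed condition. The patient is eligible (3.2), is outside the 2.2.1 list, and is therefore in the comparator, because 2.2.1 and 2.2.2 offer only two groups. The 3.2 note adds a separate analysis but does not take the patient out of that comparator.

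**Possible size**

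The plan states no figure for this subgroup, so there is nothing to reproduce. The one input from the documents is the total of 42 patients (sections 4.4 and 10.1). Assumed, because the plan is silent: n = 6 or 10 patients meet the 2.2.1 list, and m = 1 to 6 others take immunosuppressants for autoimmune disease.

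Let d be the true difference in mean change between listed and truly non-immunosuppressed patients, and let f = m / (42 − n). If the m patients change as the listed patients do, the comparator mean moves by f × d and the observed difference is (1 − f) × d. The shrinkage is f:

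| m | n = 6 (comparator 36) | n = 10 (comparator 32) |
|---|---|---|
| 1 | 1/36 = 2.8% | 1/32 = 3.1% |
| 2 | 2/36 = 5.6% | 2/32 = 6.3% |
| 4 | 4/36 = 11.1% | 4/32 = 12.5% |
| 6 | 6/36 = 16.7% | 6/32 = 18.8% |

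**Power, for illustration**

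Assume d = 1 SD, equal SDs, two-sided 5%, and power = Φ(difference / √(1/n₁ + 1/n₂) − 1.96). Take n = 10 and m = 4.

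- As written: 0.875 / √(1/10 + 1/32) − 1.96 = 0.875 / 0.362 − 1.96 ≈ 0.46, so power is about 68%.
- Regrouped, 14 against 28: 1 / √(1/14 + 1/28) − 1.96 = 1 / 0.327 − 1.96 ≈ 1.10, so power is about 86%.

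Across m = 1 to 6, power is 47–60% as written against 68–83% regrouped when n = 6, and 61–76% against 81–88% when n = 10. Part of the gain comes from enlarging the smaller group.

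**If the equal-response condition fails**

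Suppose the m patients change like the comparator instead. The present grouping then loses nothing. Regrouping would dilute the contrast to n / (n + m), which for n = 10 and m = 4 is 10/14 = 71% of d.

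**The case against.** A sponsor may define a subgroup narrowly, and section 1.1 is epidemiological background on who develops the cancer, not an analysis definition. The listed group is already mixed, so there is no guarantee that autoimmune patients respond as it does. Imprecision will also outweigh the bias: with 10 against 32 patients and equal SDs, the 95% confidence interval half-width is 1.96 × √(1/10 + 1/32) = 0.71 SD, while a 12.5% dilution of a 1-SD difference is 0.125 SD, under a fifth of that. All of this stands. It limits the size and severity of the point but does not reconcile the sections.

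Four stronger readings are tempting, and the documents do not support them:

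- *The plan says that these patients belong in the comparator.* No sentence says so. It follows from a closed list and a two-way split.
- *Several sections call them immunosuppressed.* Only section 1.1 does so expressly. The 3.2 note does not use the word, and it covers autoimmune disease whether treated or not.
- *The size of the bias is known.* The plan gives no count of such patients and no evidence on how they respond.
- *The primary analysis is compromised, or the disease-free survival model needs this variable.* The primary grouping is by lymphocyte count and does not use the subgroup. An added covariate would not repair a comparison of immune change, and it would cost a parameter in a model planned around 23 events.

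**Conclusion.** The point holds as an inconsistency with a real consequence: a rule followed as written can put pharmacologically immunosuppressed patients in the non-immunosuppressed group, and nothing elsewhere corrects it. The effect is confined to one secondary subgroup comparison, so it should be fixed but does not threaten the study. Its size is unknown. The 3–19% range rests on assumed counts (1 to 6 such patients, 6 to 10 listed patients) and on the condition that these patients change under radiotherapy as the listed ones do; if they do not, the dilution is smaller and may be nil. The need for one reconciled definition does not depend on those figures.

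**What to change.** Use one definition in sections 2.2.1, 2.2.2 and 3.2 that:

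1. adds systemic immunosuppressive therapy for autoimmune disease to the 2.2.1 list, in line with section 1.1;
2. states how autoimmune disease without such therapy is classed, since the 3.2 note includes those patients and the 2.2.1 list does not;
3. states whether the 3.2 subgroup is the same subgroup or a second one under its own label.

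Settle this before any analysis of immune change, which means before the interim analysis that section 4.3 places at 24 months.

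The cost is a few lines in three sections. Medical history is already taken at screening (section 11); the eCRF should record the therapy and its indication. The small downside is a more mixed subgroup, which could weaken the contrast if autoimmune patients respond differently. Reporting the comparison under the present 2.2.1 list as a sensitivity analysis covers that.
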